This is a multi-reader methodological study comparing the diagnostic value of 68GaPSMA-HBED-CC PET/CT or 68Ga-PSMAHBED-CC PET/MRI over MRI alone, using histologic confirmation or serial follow-up for up to 3 years as the gold standard for determination of primary prostate cancer or prostatic cancer recurrence/metastasis. Patients at moderate- to high-risk for metastatic disease who are scheduled for (the below outlines the patient cohorts recruited for this study): 1. High risk primary disease with planned surgical extirpation and lymph node dissection (oligometastatic disease) 2. Presumed intermediate or high-risk primary disease with planned targeted prostate biopsy 3. Conventional imaging equivocal or suggestive of metastatic disease, with planned biopsy of presumed metastasis a) PSA less than 0.5 ng/mL b) PSA greater than 0.5 ng/mL 4. Planned focal therapy of intermediate- to high-risk primary lesion. 5. Elevated PSA with no conventional imaging suggestive of metastatic or recurrent disease a) PSA less than 0.5 ng/mL b) PSA greater than 0.5 ng/mL. The purpose of the study is to compare 68Ga-PSMA-HBED-CC PET to conventional MRI. We hypothesize that this will demonstrate the superiority of 68Ga-PSMA-HBED-CC PET to MRI for sensitivity, and the non-inferiority of 68Ga-PSMA-HBED-CC PET to MRI for specificity. This is a paired, case-control design that is appropriate to statistically evaluate the difference in sensitivity and specificity between the two imaging modalities. Therefore, the estimation of Therefore, the estimation of population prevalence is not a study objective, and estimation of clinical utility through calculation of positive and negative predictive

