values is not appropriate. Imaging studies and follow up subject scans will be organized so that a panel of independent readers will evaluate the MRI and PET studies to assess the level of suspicion for prostate cancer (see attached statistical methods for more details). The imaging data will be encoded and archived within IDEAL. The non-imaging data collected will be encoded and archived in a RedCap database. Participants will have 1-2 visits. During visit 1 they will receive a single IV dose of 68Ga-PSMA-HBED-CC (study drug) followed by either a PET/MRI scan or, in the event that an MRI cannot be performed concurrently and/or the subject has already undergone an MRI of the abdomen/pelvis or pelvis only, a PET/CT scan 1-3 hours after injection. The PET/MRI will be a combination of standard of care and research (the MRI portion is standard of care but the PET is for research only). The PET/CT scan will be for research purposes only. All subjects will have vital signs assessed before and after study drug injection for safety purposes (not as a research procedure). Histopathological assessment will be performed, as standard of care, on tissue obtained from either RP, with or without EPLND, or biopsy of either the primary lesion or presumed metastases, within two weeks of study drug dosing, where indicated; such standard of care data will be reviewed via chart review. All subjects will be followed via chart review for three years after their visit 1 scan. 68Ga-PSMA-HBED-CC image data will be evaluated for visible uptake and compared with histopathology. Both 68Ga-PSMA-HBED-CC PET and MRI (or CT) image data will be individually assessed for appropriate staging. In the event that subjects undergo focal therapy and are scheduled to receive a post-treatment MRI as standard of care, they will be asked to participate in an optional, second posttreatment visit performed the same way as visit 1 (pre-treatment MRI); a single IV dose of 68Ga-PSMA-HBED-CC (study drug) followed by a PET/MRI scan, 1-3 hours after injection. Please note, in the event that subjects undergoing focal therapy receive a PET/CT instead of a PET/MRI, they will not have the option of participating in a second visit.

INCLUSION AND EXCLUSION CRITERIA

INCLUSION CRITERIA

1. Male aged 21 years or older.
2. Ability to provide signed informed consent and willingness to comply with protocol requirements.

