The primary endpoint is to assess the sensitivity and specificity on per-subject basis between the diagnosis from MRI and 68Ga-PSMA-HBED-CC. Based on the previous literature, we anticipate a 0.58 sensitivity and a 0.82 specificity that are consistent across all seven scenarios based on MRI. Here, we first assume that an increase in sensitivity of 30%, i.e. 0.75 under 68Ga-PSMA-HBED-CC will provide little benefit over existing MRI approach. Therefore, our statistical test for 68Ga-PSMA-HBED-CC sensitivity will be based on the null hypothesis of a value as 0.58 with the alternative hypothesis of at least 0.75. The sample size calculation is based on a Wald-test statistic under an arcsine transformation of proportion and an effective size 0.36. As a result, a sample of 34 true positive patients will give us 80% power to reject the null hypothesis at a onesided 0.1 significance level. In terms of specificity, we will expect a non-inferior performance from 68Ga-PSMA-HBED-CC compared with MRI. By assuming delta to be the estimated difference in the specificity between MRI and 68Ga-PSMA-HBED-CC, the statistical test for this metric will be constructed under the null hypothesis that the actual difference is larger than delta and the alternative hypothesis of that is smaller or equal to delta. The test statistic will asymptotically follow a normal distribution based on based on a restricted maximum likelihood estimation approach with the sample size obtained by a Wald-test statistic. Assuming delta=0.15, a sample of 12 true negative (TN) patients will allow us 80% power for this a one-sided 0.1 significance level test. In summary, we need a total of 46 patients (34 TP, 12 TN) for each scenario, leading to a total of 322 patients. Since we expect a 20% drop-off rate, we therefore intend to recruit 402 subjects. The sensitivity and specificity for the diagnosis under 68Ga-PSMA-HBED-CC and MRI on a per patient basis will be summarized as descriptive statistics and the two-sided 90% confidence intervals (CIs) will be constructed using the Wilson score method. The superior of 68Ga-PSMA-HBED-CC MRI for detection of metastatic prostate cancer will be determined if two of the three readers show statistically significantly better performance on sensitivity based on the McNemar test of discordant pairs for subjects and a non-inferiority specificity performance based on overlapped confidence intervals. The lesion-level data will be analyzed by McNemar's test adjusted for clustered data (each subject will contribute at least one lesion result, and possibly many lesion results). Published methods will be used for the lesion-level analyses (Durkalski et al, Statist. Med. 2003; 22:2417-2428 "Analysis of clustered matched-pair data"; Statist. Med. 2003; 22:279-290 "Analysis of clustered matchedpair data for a non-inferiority study design"). Reader-specific sensitivities and specificities will be calculated primarily for patient-based results for lymph nodes of any size. Sensitivity and specificity calculations will be performed for each imaging modality with the CIs calculated based on Wilson score method. In addition, we will assess 68Ga-PSMA-HBED-CC PET and MRI image data for cancer staging and compare their performance based on a Wilcoxon signed-rank test. And finally, safety of the 68Ga-PSMA-HBED-CC test will be assessed by tabulation of any procedure-related adverse effects.

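### The staging comparison names a Wilcoxon signed-rank test but no reference stage; applied to the paired stages, it shows which modality stages higher, not which is more accurate

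*Combined protocol and SAP*

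**What the plan says.** The staging analysis is one sentence near the end of the statistical text (heading not shown). After the primary and lesion-level analyses, the plan will "assess 68Ga-PSMA-HBED-CC PET and MRI image data for cancer staging and compare their performance based on a Wilcoxon signed-rank test". It does not give the staging system, the variable to be paired, a reference stage, the direction that counts as better, an alpha or a sample size.

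The Study Design section adds how the data arise: "PET and MRI (or CT) image data will be individually assessed for appropriate staging". These separately read stages are the only staging data described.

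The trial has a reference standard, histology or follow-up of up to 3 years, but it serves "as the gold standard for determination of primary prostate cancer or prostatic cancer recurrence/metastasis". That is presence of disease, not stage. The comparison with pathology in Study Design concerns PET uptake: PET "image data will be evaluated for visible uptake and compared with histopathology". Neither statement is tied to the staging test.

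**The concern.** A statement about staging performance is a statement about agreement with the true stage. A signed-rank test on two assigned stages has no access to the true stage. It asks whether one modality tends to assign a higher stage than the other, and gives the same answer whether the higher stages are right or wrong.

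Two errors could follow. A modality that over-stages could be reported as performing better. Conversely, a modality that is much more accurate could show no difference, because the other modality's errors fall evenly on both sides and cancel.

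There is a smaller point about the comparator. The statistical text names MRI, while Study Design allows MRI or CT. A comparison of PET with the CT of a PET/CT would not answer the trial's question, which is PET against MRI.

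**Working it through.** The plan gives no figure for the staging comparison, so there is nothing to reproduce. The check is algebra followed by simulation.

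**Algebra.** Let T be the true stage, e_P the signed PET error and e_M the signed MRI error, in stages.

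- Raw paired difference: (T + e_P) − (T + e_M) = e_P − e_M. T drops out, and only signed errors remain.
- Accuracy depends on whether each error is zero, or on its size. A paired accuracy score is |e_M| − |e_P|, which is positive when PET is closer to the truth.

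The two quantities can differ in sign.

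**Inputs.** For scale, n = 46 and one-sided alpha 0.1 are borrowed from the sizing of the sensitivity and specificity tests ("we need a total of 46 patients (34 TP, 12 TN) for each scenario, leading to a total of 322 patients"; "80% power to reject the null hypothesis at a onesided 0.1 significance level"). The plan does not state them for staging. All error rates below are assumptions.

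**Simulation 1** (2,000 trials, n = 46, one-step errors, true stage away from the ends of the scale).

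| Case | Mean shift, PET minus MRI | Accuracy, PET minus MRI | Signed-rank on raw stages: PET higher | McNemar on correct stage: PET better |
|---|---|---|---|---|
| A. PET 70% correct, all errors high; MRI 80% correct, all errors low | 0.30 − (−0.20) = +0.50 | 70 − 80 = −10 points | about 100% | under 1% |
| B. PET 90% and MRI 60% correct, errors symmetric | 0 − 0 = 0 | 90 − 60 = +30 points | 8% to 10% | 97% to 98% |
| C. PET 90% correct, symmetric; MRI 70% correct, all errors low | 0 − (−0.30) = +0.30 | 90 − 70 = +20 points | about 99.5% | about 81% |

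Ranges cover repeated runs. In case B the raw-stage test rejects at about its own alpha. A signed-rank test on absolute distance detects the gain in about 98%. In case C the raw-stage test points the right way.

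**Simulation 2** (1,000 trials, n = 46, four ordered stages with assumed true shares 0.35, 0.30, 0.20 and 0.15, one-step errors, no staging beyond the ends of the scale).

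- PET over-stages with probability 30%, MRI error-free (about 75% against 100% correct, since the top stage cannot be over-staged). Raw stages: PET higher in 100%. Absolute error: PET favoured in 0%, MRI in 100%.
- PET over-stages with probability 30%, MRI errs 5% up and 5% down (about 74% against 92% correct). Raw stages: PET higher in 98%. Absolute error: PET favoured in 0%, MRI in 88%.
- PET error-free, MRI over-stages with probability 20%. Raw stages: PET higher in 0%, MRI higher in about 100%. Absolute error: PET favoured in about 100%.
- PET error-free, MRI errs 15% up and 15% down. Raw stages: PET higher in 5%, MRI higher in 20%. Absolute error: PET favoured in 100%.

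In the last case MRI comes out higher more often because patients at the lowest stage, the largest group, cannot be under-staged. With n = 322 the first case is unchanged. In the last, MRI is higher in 44% and PET in 0.5%, so more subjects do not repair the raw-stage test.

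**Comparator.** The statistical text names MRI. Inclusion criterion 5b requires a clinically indicated MRI within 3 months before treatment for the PET/CT cohort, and exclusion criteria 4 to 6 remove PET/CT subjects whose earlier MRI is missing or below the quality standard. An MRI should therefore exist for every eligible subject, and the mention of CT in Study Design needs only to be reconciled.

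**The case against.** The strongest reply is that the plan never says raw stages are paired. It speaks of performance, and a signed-rank test on error scores against a reference would also satisfy the sentence. This is right as far as it goes. But the plan defines no such score and no reference stage. Where truth does enter a comparison, for sensitivity and specificity, the plan names those measures and uses McNemar. Separately read stages remain the natural input. If error scores were intended, the score and the reference they need are missing and could be chosen after the data are seen.

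A reader might infer that the plan will count over-staging by PET as superior performance. The documents do not support this: nowhere is a higher stage called better. What stands is that, with no direction defined, a result in favour of higher PET stages could be read that way.

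The failing cases were also chosen to fail. The introduction describes conventional MRI as only intermediately sensitive for nodal metastases, which suggests MRI under-staging. Case C has that form, and there the raw-stage test favours the more accurate modality. This stands as a limit on size: the test is not always misleading, but its result alone does not show which case applies.

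A reader might also infer that PET will be tested against CT. The analysis sentence names MRI only, and the eligibility criteria require an MRI in the PET/CT cohort, so this is an inconsistency of wording.

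Finally, the analysis is additional, with no power claim or decision rule. That stands and limits the weight of the point.

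**Conclusion.** The concern holds in conditional form. The paired variable, the reference stage and the direction of benefit are not specified. If the test is applied to the only staging data described, it measures a shift in assigned stage and cannot support a statement about performance. That much follows from the algebra and needs no assumption about error rates.

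The size does rest on assumptions. In the cases examined, the raw-stage result ranges from pointing the wrong way in about 100% of trials, through rejecting at about alpha despite a 30-point accuracy gain, to pointing the right way when MRI under-stages.

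The superiority decision rests on per-subject sensitivity and specificity, so the primary conclusion is unaffected. The point is still worth correcting before the data are read, since the staging result would otherwise be reported as a comparison of performance.

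**What to change.** 1. Define the staging system and a reference stage from histology or follow-up, and state which subjects have one.
2. In those subjects, score each modality's stage as correct or incorrect and compare with McNemar's test. Alternatively, apply the signed-rank test to the absolute distance from the reference stage, with closer to the reference defined as better. State alpha and sidedness.
3. Report over-staging and under-staging separately for each modality.
4. If a signed-rank test on the raw stages is kept, describe it only as a shift in assigned stage.
5. Reconcile the comparator in Study Design with the statistical text: MRI in every subject, using the prior MRI that eligibility requires in the PET/CT cohort.

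The cost is more than a change of wording. The analysis is limited to subjects with a reference stage. Histology is available only where indicated, node dissection is optional, and biopsy of a single site may not establish a full stage. The plan should say how follow-up fills that gap, and report how many subjects in each cohort contribute. No additional scans or visits are required.

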3. Pathologic confirmation of adenocarcinoma of the prostate gland or high clinical suspicion (PSA > 4 ng/mL, or PSA density > 0.15 ng/mL2, or PSA doubling time < 2 years).
4. Meet one of the following 5 Criteria:
 - a. Planned for surgical extirpation, which may or may not include lymph node dissection (high risk primary disease)
 - b. Planned for targeted biopsy of primary lesion
 - c. Conventional imaging equivocal or suggestive of prostate cancer metastasis/es
 - d. Planned focal therapy (with or without radiation therapy) with serial follow-up
 - e. Elevated PSA with no conventional imaging suggestive of metastatic or recurrent disease

5. a. If part of PET/MRI cohort, subject will undergo clinically indicated MRI imaging prior to treatment.
Or b. If part of PET/CT cohort, subject will have had clinically indicated MRI within 3 months prior to treatment.

6. Participants must agree to use an acceptable form of birth control throughout the study period. Participants must use condoms for a period of seven days after each injection, if engaged in sexual activity."

EXCLUSION CRITERIA

1. Clinical and/or technical factors that would compromise statistical analysis of the PET and/or MRI.
2. If part of PET/MRI cohort and patient cohort 3 or 5, subject does not plan to have a prescribed abdomen2/ MRI
3. If part of PET/MRI cohort and patient cohort 1, 2 or 4, subject does not plan to have a prescribed pelvis MRI
4. If part of PET/CT cohort and patient cohort 3 or 5, subject does not have previous MR imaging of abdomen and pelvis
5. If part of PET/CT cohort and patient cohort 1, 2 or 4, subject does not have previous MR imaging of pelvis
6. If part of PET/CT cohort, investigator review determines that previous MR images do not meet institutional quality standards
7. If part of PET/MRI cohort, contraindications to MRI
8. Contraindications to PSMA IV administration
9. Other unspecified reasons that, in the opinion of investigators, make the subject unsuitable for enrollment

DATA AND SAFETY MONITORING PLAN

Data is recorded both electronically and in paper format Data will be kept in the PIs locked office Data will be kept on a password-protected computer Data will be saved on a secure server.

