The study will be stopped if there are any serious adverse events related to any of the study procedures, but this is not anticipated. However, subjects who experience an AE of grade 3 or higher will be reviewed and removed from the study. Vital signs will be obtained before and after the dose administration.

This study will follow standard operating procedures for reporting adverse events and utilize the AE grading from Terminology Criteria for Adverse Events v4.0. AE grading will be defined as the

following categories: Grade 1- Mild; asymptomatic or mild symptoms; clinical or diagnostic observations only; intervention not indicated. Grade 2- Moderate; minimal, local or noninvasive intervention indicated; limiting age-appropriate Activities of Daily instrumental Living. Grade 3- Severe or medically significant but not immediately life-threatening; hospitalization or prolongation of hospitalization indicated; disabling; limiting self care Activities of Daily Living. Grade 4- Life-threatening consequences; urgent intervention indicated. Grade 5- Death related to AE.

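### The only planned safety table admits adverse events already judged procedure-related, while the monitoring plan grades adverse events and acts on severe ones whatever their cause

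*Combined protocol and SAP*

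**What the plan says.** All references are to the combined protocol and SAP.

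- **Statistical section (heading not shown), last sentence.** The one safety analysis is described as follows: "safety of the 68Ga-PSMA-HBED-CC test will be assessed by tabulation of any procedure-related adverse effects". No all-cause table or listing is described anywhere.
- **Data and Safety Monitoring Plan, reporting and grading.** "This study will follow standard operating procedures for reporting adverse events and utilize the AE grading from Terminology Criteria for Adverse Events v4.0". The five grades are then defined, up to death.
- **Data and Safety Monitoring Plan, actions.** The removal rule has no relatedness condition: "subjects who experience an AE of grade 3 or higher will be reviewed and removed from the study". The study stop does have one: "The study will be stopped if there are any serious adverse events related to any of the study procedures".
- **Data and Safety Monitoring Plan, scheduled measurement.** "Vital signs will be obtained before and after the dose administration". The Study Design section repeats this and labels the measurement as non-research.
- **Study Design, follow-up.** "All subjects will be followed via chart review for three years after their visit 1 scan". Use of this review to find adverse events is neither stated nor excluded.
- **Study Design, tissue and second visit.** Where indicated, histopathology uses surgical or biopsy tissue obtained within two weeks of dosing. Focal-therapy subjects imaged by PET/MRI may have an optional second injection and scan, run in the same manner as the first.

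**The concern.** Relatedness is normally a reported attribute of an adverse event. Here it decides whether the event is counted at all. The table then shows the outcome of a judgement, and a reader cannot see what that judgement left out.

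Two features of the design make the judgement hard to verify. Every subject is dosed, so there is no background rate to compare with. Many subjects also have surgery or a biopsy close to the injection, which offers a ready alternative explanation for an event in that period. The documents name no relatedness criteria and no assessor.

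At stake is how the safety result can be read. A sparse table could mean few events, or several events attributed elsewhere, and the planned output cannot separate the two.

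**Working it through.** The plan states no safety figure, so there is none to reproduce. The check sets the safety statements side by side and follows each type of recorded event through them.

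| Recorded event | Graded under CTCAE v4.0? | Reviewed, subject removed? | In the planned safety table? |
|---|---|---|---|
| Grade 3–5, judged procedure-related | Yes | Yes | Yes |
| Grade 3–5, judged not related | Yes | Yes | **No** |
| Grade 1–2, judged procedure-related | Yes | No | Yes |
| Grade 1–2, judged not related | Yes | No | **No** |
| Any grade, delayed, recorded and judged procedure-related | Yes | By grade | Yes: no time limit is stated |

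**Row 2 is the mismatch.** The monitoring plan treats the event as serious enough to review and to remove the subject, yet the analysis drops it. The events acted on are wider than the events reported.

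**Row 5 limits the finding.** A delayed event is admitted once it is recorded and attributed. What is missing is assurance that it will be recorded. Vital signs around the injection are the only scheduled safety measurement, no collection window is given, and chart review is not expressly assigned to adverse events.

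**What an empty table would mean (context only).** The inputs are 402 planned recruits and 322 after the expected 20% drop-off, both from the statistical section. With no events among *n* dosed subjects, the exact one-sided 95% upper bound on the event rate is 1 − 0.05^(1/*n*):

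- *n* = 402: 1 − 0.05^(1/402) = 0.0074, or 0.74%
- *n* = 322: 1 − 0.05^(1/322) = 0.0093, or 0.93%

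The plan claims no such bound. If a reader computed one, it would apply only to events that were both captured and judged procedure-related. It would not bound the rate of all adverse events after injection.

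The size of the gap between those two rates cannot be calculated. The documents give no event rate, no capture fraction and no rate of misattribution.

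**The case against.** The strongest reply is that the study evaluates an imaging agent and safety is its last, purely descriptive item, with no safety hypothesis. Leaving out an event the injection did not cause loses no drug-related event, and an all-cause table without a comparator will carry much surgical and biopsy background. The procedures that govern adverse-event reporting may also set a window and name an assessor, and we cannot see them. Much of this stands, and it is why the point is minor. It does not answer the mismatch: reporting procedures govern what is reported, while the statistical section still limits what is tabulated. Nor does it help when a related event is wrongly attributed to surgery or biopsy.

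A reader might infer several stronger claims that the documents do not support:

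- **That delayed events cannot enter the result.** The analysis sentence has no time limit, reporting follows standard procedures, and charts are reviewed for three years.
- **That the non-research label on vital signs closes off adverse-event reporting.** The label classifies one measurement. Nothing says vital signs are the source of the table.
- **That the second injection is unobserved.** That visit follows the same procedure as the first, and chart review running from visit 1 covers any second visit within its three years.
- **That the stopping and removal rules are weakened.** They act on reported events and do not depend on how events are tabulated.
- **That the protocol already implies a seven-day safety window.** The text concerned is a contraception instruction: "Participants must use condoms for a period of seven days after each injection, if engaged in sexual activity". It does not define a risk period for adverse events.

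**Conclusion.** The point holds in a narrow form. Events not attributed to a procedure are excluded from the only planned safety table, although the monitoring plan grades adverse events and acts on those of grade 3 or above regardless of cause. Capture of delayed events is not assured, but such events are not barred.

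The exclusion follows from the wording and needs no assumption. The view that it could matter assumes that some attributions will be uncertain. That is reasonable with no undosed comparator and with surgery or biopsy near dosing, but it applies less to subjects who have neither. No magnitude can be given. Assumed capture fractions would produce numbers without measuring this defect.

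This is a minor improvement to a descriptive safety output. The primary sensitivity and specificity analyses are unaffected. The absence of a stated window, assessor and relatedness definition is missing detail and not an error in itself.

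**What to change.** Replace the last sentence of the statistical section with wording to this effect:

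> All adverse events recorded under the Data and Safety Monitoring Plan or found in the planned chart review, within a window after each injection (visit 1 and the optional visit 2) that the sponsor specifies in advance, will be tabulated by CTCAE v4.0 grade. Relatedness will be shown as a column, and the procedure-related subset will be presented beside the full table.

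The sponsor should choose and justify the window. The stopping rule, the removal rule and the non-research status of vital signs need no change for this.

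**Cost.** One analysis sentence changes, and adverse-event fields are added to the chart abstraction. Someone must abstract the events and record relatedness for up to 402 subjects, which is real work but needs no new visit or procedure.

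**Downside.** Background surgical and biopsy events will appear, which is why the related subset must sit beside the full table. Mild events that were never charted will still be missed.
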